### **Reducing Sound Therapy**

*(End of treatment, in this case, will mean reducing the use of SGs and enriched environmental sound. Study Participants will, however, be required to continue to complete all TRTT Follow-up Visits and required ATH evaluations and psychometric measures. This also allows the Study Audiologist to monitor the stability of the treatment effects.)*

To terminate treatment, it is important not to make rapid changes. In stopping the use of SGs, it is important to let the Study Participants know not to wear them intermittently, i.e., for several shorter periods each day (on/off) (*This draws attention to the symptoms*). Rather, they should stop wearing the devices certain days of the week (e.g., weekends) and then gradually stop the use of sound enrichment in the same way.

Finally, Study Participants can stop the use of enriched sound at night, although many individuals prefer to continue use of enriched sound at night as it helps them to sleep. They can continue to use the instruments periodically if considered necessary.

For Study Participants with tinnitus and hyperacusis, the hyperacusis is treated first with generally good results within the first 6 months. For some Study Participants with tinnitus and hyperacusis, when the hyperacusis is no longer an issue, the tinnitus is significantly improved.

If Study Participants reach this point before nine months of full TRT treatment, they should be required to wear the SGs and use enriched environmental sound for at least nine months.

---

---

## Chapter 12

#### 12.1 Introduction

Sound therapy (ST) is an integral component of the Tinnitus Retraining Therapy (TRT) treatment (Jastreboff *et al.*, 1996). The goal of ST is to facilitate the habituation process, which is initiated by directive counseling (DC; described in Chapter 11). ST is hypothesized and intended to decrease the contrast between tinnitus-related neuronal activity and background neuronal activity, to interfere with the detection of the tinnitus signal, and to decrease the gain within the auditory pathways. ST is implemented with a low-level, relatively broad-band, neutral sound. The most convenient way to provide this sound is to use commercially available sound generators (SGs) fit to both ears, supplemented by environmental sound. The Tinnitus Retraining Therapy Trial (TRTT) will test the efficacy of using ST as an adjunct to DC in TRT. Study Participants will be randomized to use of a standard or placebo SG.

#### 12.2 Sound Generators

We will use a digital equivalent of the Tranquil model sound generator, manufactured by General Hearing Instruments, Inc. (GHI), as the SG for the TRTT. The new digital devices will be implemented with added features including data-logging capability to enable the Study Audiologist to monitor the Study Participant's use of and compliance with the SG. Additionally, each participant's sound-level exposure will be monitored and logged to determine whether the SGs or environmental sound is the primary sound exposure and the nature of the sound-exposure properties. The SG will be housed either in a behind-the-ear (BTE) instrument or in an all-in-

the-ear (ITE) non-occluding device, both of which will offer adjustment of the output volume to a “zero” (fully quiet) noise floor. GHI will provide both the standard and the placebo SG devices. The placebo SG will have specially designed sound properties, closely resembling key properties of the standard SG, and a physical appearance identical to the standard (conventional) instrument so that neither the Study Audiologist nor the Study Participant will be aware of which sound treatment the participant is receiving.

### **12.2.1 Sound Generator Assignment**

Subsequent to completion of the baseline testing and determination of eligibility of the Study Participant, including informed consent, the Clinical Center will request from the DCC the randomized treatment assignment for the Study Participant using the online randomization protocol. At randomization, the Randomization Registration Form will include a kit ID. SGs will be assigned to Study Participants assigned to TRT. If the assigned SG is a BTE device, the pair of SGs will be included within the kit. The serial number of the devices will be located on the box containing the BTE devices. If the assigned SG is an ITE device, the kit will contain a Sound Generator Order Form with the serial number printed on the form and the Clinical Coordinator or Study Audiologist will order custom SG treatment devices from GHI for the Study Participant. The ordering and production of ITE devices requires the making of outer-ear impressions for the customized SGs, as described in Section 12.2.2. The assigned pair of SG devices will be fitted to the Study Participant and activated at Treatment Visit 1 (T1), immediately after the DC session as described in Section 12.2.3. The Sound Generator Issue Form documents which pair of devices is issued to the Study Participant and should be completed at T1. T1 may follow on the same day as randomization, if time permits.

### **12.2.2 Ear Canal Impressions**

Most Study Participants who meet eligibility criteria for inclusion in the study and who willingly agree to participate will have outer-ear-canal impressions made bilaterally subsequent to completing informed consent. This activity may be performed at the Baseline Visit or during a subsequent Randomization Visit at the discretion of the Study Audiologist.

The Study Audiologist will take impressions of both of the Study Participant’s outer-ear canals following the checklist and protocol outlined in Table 1. The first step in taking the impressions is to explain to the Study Participant how an impression is made and the purpose of taking an impression. This explanation will allay any fears that he or she may have about the procedure. The Study Audiologist will inform the Study Participant that the impression of the outer-ear canal is made with a soft material that must set up for about ten minutes. It also is important to explain that in some cases the first impression of the ear canal with the jaw open will not produce a good fit, and that a second impression will be taken with the jaw closed to

assure a good and comfortable fit with one of the two sets of impressions. The Study Participant will be instructed to continue to wear his or her glasses and dentures, if these are present, during the impression-taking protocol. Occasionally, it may be necessary to make a second impression for one or more of these opened- or closed-jaw conditions. If the definition of the completed impression does not adequately capture the anatomy of the outer ear and ear canal.

The Study Audiologist will then gather the materials and tools needed to take the impression, and place a bite-block between the molars for the open-jaw impressions. Next, an examination of the ear canal will be conducted using an ear light or an otoscope to assess the:

- Size of the impression needed;
- Length, direction, and diameter of the ear canal;
- Shape and contours of the external ear and canal; and
- Presence of any impediment to taking an impression (e.g., wax, enlargement, trauma, etc.).

If there is hair growth in the ear canal, it should be trimmed with scissors. A foam ear-canal block is then placed in the ear canal to extend just beyond the second bend of the canal. The ear-canal block must completely occlude the full diameter of the ear canal. If the Study Participant has a surgically altered ear canal, then the ear block must be placed by a physician before taking the impression. The ear-canal block serves to:

- Prevent impression material from reaching the eardrum;
- Acts as a safety catch if impression material sticks in the canal; and
- Assures a completed canal cross-section.

Ear-canal blocks may be trimmed with scissors for narrow ear canals. For large ear canals, larger ear canal blocks or sometimes more than one are block may be used. The ear canal block must be compressed for a proper fit with the attached removal thread extending past the outer ear. Blocks for both ears may be prepared and inserted at this point to expedite the placement of the impression material in each ear as described below.

The Study Audiologist then prepares the material used to make the impression. In the TRTT, silicone will be used to make the impressions for the SGs. Silicone is flexible yet has total memory, does not sag or collapse, and generally is not damaged by handling or shipping. Silicone also is easy to manipulate and to insert. Silicone impression material supplied by GHI will be

used in the TRTT. The manufacturer's directions for mixing the material should be carefully followed and the silicone loaded into a syringe or "gun" for placement of the impression material in the ear. The quicker the material can be placed in the syringe and the procedure started, the better the impression.

After placing the silicone material in the barrel of the syringe, the Study Audiologist will insert the plunger and force a small amount of the material into the nozzle to remove air pockets. The Study Audiologist will then place the syringe near the canal block and begin to inject the material. The tip of the syringe must be kept in the impression material at all times. As the impression material becomes visible, the syringe is slowly withdrawn simultaneously with injection of additional material. The process of inserting the impression materials continues until the helix and concha areas are completely covered and then the tragus is covered.

When the external ear has been filled completely, the Study Audiologist will use his or her finger (not palm) to touch and gently smooth the impression material in the concha and helix areas. It is critical to fill the helix, but care should be taken not to overfill the impression material, which may distend the outer ear and confound the mold of the outer ear and ear canal. Subsequently, an impression is made immediately for the opposite ear so that both impressions can cure simultaneously. After an adequate period to allow the impression material to set, the ear canal impression should be removed.

To remove an impression, the Study Audiologist will gently press the ear away from the impression; remove the helix curl slightly and bring the impression straight out while holding the ear canal block thread. It is best to pull gently and steadily so as not to distort the impression. After the cured impressions are removed from the ears, and otoscopic examination should be performed to ensure that all impression material has been removed from each ear and confirm that there are no abrasions of the ear canals or ear drum as a consequence of performing the protocol.

The Study Audiologist will then check to make sure that the impression adequately mirrors the outer-ear canal and that each helix and concha are well-formed along with the external ear canal portion. If an impression is flawed, then it will be necessary to take a second impression. If it is adequate, then the impression will be labeled and prepared for shipping to GHI. The protocol then will be repeated for the closed-jaw condition, but with the bite-block removed from the mouth.

Each impression should be labeled either either "opened-jaw" or "closed-jaw" and either "left" or "right" ear. The shipment of the impressions to GHI will therefore include two sets of impressions for each ear as well as a Sound Generator Request Form identifying the Study Participant and including the address to which the devices should be sent. Impressions will be

shipped by Federal Express overnight delivery to ensure preparation and return of the SG from the manufacturer to the Clinical Center in time for the Initial Treatment Visit (T1). At the time the impression is sent from the Clinical Center, both the DCC and GHI will be notified and, similarly, upon return of the SGs to the Clinical Center, the DCC and Clinical Center will be notified of shipment.

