### **21.3.3 Distribution of Devices**

At the beginning of the study, the TRTT used behind-the-ear devices and the DCC was responsible for distribution of devices to Clinical Centers. GHI sent a sufficient number of pairs of SGs to the DCC to supply all 6 Clinical Centers with the first 6 randomized treatment assignments. Each SG pair is housed in a single container.

The DCC placed each container within a box having a kit ID. Each box had a sheet of paper noting the treatment assignment, either TRT (Directive Counseling and Sound Therapy) or Standard of Care (SC). Boxes for Study Participants assigned to TRT also contained the pair of SGs assigned to that Study Participant. The DCC affixed a tear-off label to each kit. The label included the kit ID and a tear-off portion to be affixed to the Sound Generator Issue Form for

Study Participants assigned to TRT or to the Standard of Care Checklist for Study Participants assigned to SC.

Figure 1. Sample tear off label

In order to maintain a constant stock of SG pairs at each Clinical Center, after a series of randomized treatment assignments involving an SG, the DCC sent an email to GHI requesting replenishment of the stock at the DCC. GHI sent the requisite SGs within two business days.

Part-way through the trial, it became obvious that for some Study Participants, the behind-the-ear devices failed at an unacceptable rate and the decision was made to preferentially use non-occluding in-the-ear devices from that point forward. The DCC will continue to send kits with tear-off labels to the Clinical Centers, but instead of including a box containing the sound generators, the kit will include a sheet of paper noting the treatment assignment, either TRT or SC, and a Sound Generator Order Form. The Sound Generator Order form will include the serial number of the assigned device and a place for the Clinical Center to indicate the preferred color for the device. When the impressions for in-the-ear devices have been obtained and are ready to be shipped to GHI, the Sound Generator Order Form is completed and faxed to both GHI and the DCC. This action notifies GHI about the requisite sound generators to be manufactured. A copy of the Sound Generator Order Form is included in the Study Participant's file, and the original placed in the box with the impressions to be shipped to GHI.

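### Section 12.2.2 lets ear-canal impressions be taken before assignment is known, so standard-of-care participants can undergo a procedure for which they have no use

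*Combined protocol and SAP*

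**What the plan says.** On who is impressed, Section 12.2.2 states: "Most Study Participants who meet eligibility criteria for inclusion in the study and who willingly agree to participate will have outer-ear-canal impressions made bilaterally". On when: "This activity may be performed at the Baseline Visit or during a subsequent Randomization Visit at the discretion of the Study Audiologist". It neither restricts the step to an arm or device type nor requires the kit to be opened first.

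Section 12.2.1 puts the assignment request after baseline work: "Subsequent to completion of the baseline testing and determination of eligibility of the Study Participant, including informed consent, the Clinical Center will request" the randomized assignment. It then states: "SGs will be assigned to Study Participants assigned to TRT". For an in-the-ear device, "the kit will contain a Sound Generator Order Form with the serial number printed on the form", and it is the making of these devices that calls for impressions. A behind-the-ear pair comes ready in the kit. Section 22.2.4 confirms that the randomization report shows only a kit ID and that the assignment itself is inside the kit.

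Section 21.3.3 records a switch, part-way through the trial, from behind-the-ear to preferential use of in-the-ear devices. It describes completing and faxing the order form at this point: "When the impressions for in-the-ear devices have been obtained and are ready to be shipped to GHI". Table 23.1 gives the SC group a recommendation to use ambient sound and no study sound generator.

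**The concern.** Followed literally, Section 12.2.2 allows a physical procedure in people for whom the trial has no use for the result. By the plan's own account the procedure is not trivial. Both ears are done in two jaw positions. A foam block that fully occludes the canal is placed just beyond its second bend, and a physician must place it if the canal has been surgically altered. Afterwards the audiologist must "confirm that there are no abrasions of the ear canals or ear drum", and Table 1 of Chapter 12 adds a check for bleeding or swelling.

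At stake is avoidable burden, mainly in SC. Because the choice is left to each audiologist, how often it happens can differ between centers.

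**Working it through.** **1. The allocation behind the one-third share.** Section 23.2.3 gives 228 participants, 76 in each of three groups. Inputs there: difference 7 TQ points, SD 12.5, two-sided alpha 0.05 divided over three comparisons (0.0167 each), power 80%, attrition 10%.

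n per arm = 2 × 12.5² × (2.394 + 0.842)² / 7² = 312.5 × 10.47 / 49 = 66.8, so 67. Then 67 / 0.90 = 74.4, so 75, and 3 × 75 = 225. A t-based calculation gives 69, then 77, and 231 in total. The plan's 228 lies between the two, so the equal split of 76:76:76 can be used.

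**2. Sequence of events, from the sections side by side.**

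| Step | Source | Arm known? |
|---|---|---|
| Baseline testing, eligibility, consent | 12.2.1 | No |
| Impressions, first permitted time (Baseline Visit) | 12.2.2 | Not if randomization is later |
| Assignment requested; kit ID issued | 12.2.1, 22.2.4 | Not until kit opened |
| Kit opened; order form or behind-the-ear pair found | 12.2.1, 21.3.3 | Yes |
| Impressions, second permitted time (Randomization Visit) | 12.2.2 | Only if after kit opening |
| Order form and impressions go to the manufacturer | 21.3.3 | Yes |

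An impression taken at the first permitted time cannot be ordered against until the kit is opened, because the serial number is on the form inside it.

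**3. SC share of those impressed.** Let f be the proportion of participants impressed before assignment. Assume that every TRT participant eventually gets an in-the-ear device and that no SC participant is impressed after assignment. Then SC impressed = 76f, TRT impressed = 152, and

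SC share = 76f / (152 + 76f) = f / (f + 2).

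| f | SC share of all impressed |
|---|---|
| 0 | 0% |
| 0.25 | 19/171 = 11.1% |
| 0.50 | 38/190 = 20.0% |
| 0.75 | 57/209 = 27.3% |
| 1 | 76/228 = 33.3% |

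Among only those impressed before assignment, the expected SC share is 76/228 = one third, whatever f is.

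**4. Counts.** Let s be the share of enrolment after the switch to in-the-ear devices, and assume no impressions before it. SC participants impressed = 76 × s × f, each with at least 2 ears × 2 jaw positions = 4 impressions. The documents give neither s nor f. For s × f = 0.25, 0.50 and 0.75 the counts are 19, 38 and 57 people, or 76, 152 and 228 impressions. The upper bound is 76 people and 304 impressions. TRT participants with a behind-the-ear pair would add to this by a number that cannot be derived.

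**5. With the fix.** SC participants impressed = 0. The sample size and power do not depend on this step and are unchanged.

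**The case against.** The strongest reply is that a Baseline Visit need not precede assignment. Section 18.5.1 has forms entered at the Baseline Eligibility visit immediately before assignment is requested, Section 14.7.4 treats the randomization forms as collected at that visit, and Section 14.9.2 speaks of randomization procedures during and after it. On that view Section 12.2.2 means: take impressions at whichever visit randomization occurs. Chapter 12 is also the sound-therapy chapter. Section 12.2.1 reaches the impressions from the step of ordering an in-the-ear device, Appendix A of Chapter 12 puts the request form in the kits of TRT participants, and 'most' could describe the two TRT arms out of three. Chapters 5 and 10, which cover randomization logistics and visits, are not in the part of the document available here and may fix the order.

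Much of this stands as a plausible account of intent. It does not remove the permission. Section 12.2.2 itself sets the Baseline Visit apart from a subsequent Randomization Visit, and nobody can pick out TRT participants before the kit is opened. Section 21.3.3's end-of-trial offer of unused devices to SC does not give early impressions a purpose either: it depends on TRT proving successful, and nothing says that impressions are kept for it.

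A reader might go further and infer a bias: the audiologist must "explain to the Study Participant how an impression is made and the purpose of taking an impression", so an SC participant prepared for a device and then given none may be let down and score worse on the self-reported TQ, to TRT's advantage. The documents do not support this as a finding. They neither mention nor size such an effect. Blinding covers only the type of sound generator, so SC participants know they have none whether impressed or not, and only an unknown increment could matter. The first follow-up TQ is at 3 months. Nor is concealment threatened, since the assignment stays in the kit.

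**Conclusion.** The point holds as one of participant burden and inconsistent text. As written, Section 12.2.2 permits impressions before assignment, and for SC participants, and for TRT participants with behind-the-ear devices, they serve no purpose. The expected SC share is one third of those impressed before assignment, given equal allocation.

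A reader might infer that one in three of all people impressed is SC. That is only the ceiling of a 0 to 33.3% range, reached if every impression precedes assignment. The head counts rest on assumed values of s and f. A reader might also infer that SC uses no device at all, but SC counseling recommends environmental sound devices and checks their use (Chapter 13, Appendix B); what SC lacks is a study sound generator. No injury rate is given, so the burden is the procedure itself and not a quantified harm. No claim is made about TQ. The conclusion would narrow to a wording correction if Chapters 5 or 10 already require assignment to be known first.

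**What to change.** Check Chapters 5 and 10, then reconcile Section 12.2.2 with Sections 12.2.1 and 21.3.3:

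- Replace the opening description of who is impressed with: *Study Participants assigned to TRT with an in-the-ear device*.
- Replace the timing sentence with: *Impressions are taken by the treating Study Audiologist only after the kit has been opened and shows assignment to TRT with an in-the-ear device; this may be on the day of the Baseline Visit if randomization occurs then.* Naming the treating audiologist also protects the second audiologist, who under Section 17.2.1 must stay blinded to assignment.
- If enrolment is under way, count the SC participants already impressed, by center.

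The cost is a change of wording in one section and the need to schedule the impression step after randomization. That should be workable on the day, because the Section 14.5 forms are completed by the participant just before assignment is requested. The device order is not held up by the order form, which is available only from the kit in either case.

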### **12.2.3 Fitting the Sound Generator**

The fitting/activation of and orientation to the SGs will take place after the DC session has been completed at T1. Typically, fitting of the SGs requires about one hour, and includes instruction to the Study Participant on the use and care for the instruments, correct volume settings, schedule of use, and insertion and removal of instruments. Because treatment counseling also takes place at this visit, a minimum of three hours should be allotted to complete T1. A checklist of the fitting protocol is included in Table 2 and a more detailed summary in Appendix A. A script for the fitting protocol, including recommendations for using SGs is included in Appendix B.

The Study Audiologist will fit the SG to each ear of the Study Participant using the instructions and protocol described below. An optimal fit will be achieved by ensuring that each instrument is seated comfortably and securely on the top of the ear for the BTE devices. There should be no gaps between the ear, the BTE sensing plate, and the head. The thin tube dome for the BTE should seat at the top of the ear canal, and the retention tubing should loop up the posterior of the concha. On very rare occasions, for patient comfort, the retention tubing may be clipped shorter. It should never be completely removed.

Similarly, the Study Audiologist will evaluate the fit of the ITE instruments to each ear of the Study Participant. The optimal fit requires the SG case to be well molded to the participant's ear, yet to be non-occluding so as to allow a pathway for environmental sound to enter and pass through the ear canal. The Study Audiologist should insert the SGs in both ears and check the fit. The SGs should comfortably and snugly fit within the ear canals so as not to dislodge when the Participant moves or shakes his or her head. Neither should the SGs be too long nor skewed. A reported sensation of discomfort from the Participant indicates an unacceptable fit, requiring repositioning of the SG within the ear or an adjustment of the SG. The Study Participant may be more aware of one device than the other; this is normal. In most cases, the Study Participant will adapt to the wear of both devices within a week. If the Study Audiologist finds that the instruments do not fit the Study Participant appropriately, then the devices will be returned to GHI for modification. New impressions must also be sent so that customized shells can be remade if necessary.

